Power Calculations: The sample size calculations for Specific Aim 1 focus on assessing differences in changes from baseline to 8 weeks in mean outcome between the PT3 and control groups. Estimates of variability and clinically relevant effect sizes for Specific Aims 1 & 2 were obtained from preliminary data for the treatment effect estimates and from [name] et al. (2013) for the comparison group effect estimates. Assuming a statistical model for a replicated randomized complete block experiment with fixed treatment factor (PT3 vs comparison) and a 0.050 two-sided significance level, the null (primary) hypothesis of no difference in mean change from baseline to 8 weeks in self-selected gait speed between groups will have 90% power to detect a difference of 0.12 m/s given a common standard deviation of 0.167 m/s with a sample size of n=24 per group. A sample size of 24 in each group will also have 79% power to detect a difference of 0.137 m/s in fast gait speed, assuming a common standard deviation of 0.127 m/s. Specific Aim 2: A sample size of 24 in each group will have 99% power to detect a difference in mean peak power of 0.819 watts/kg with a common standard deviation of 0.485 watts/kg with a 0.050 two-sided significance level. A sample size of 24 in each group will have 90% power to detect a difference in mean fascicle length of 1.55 cm given a common standard deviation of 1.61 cm. Specific Aim 3: Average number of strides per day (over a 5 day period) were obtained from [name] et al. (2014) with the differences observed between GMFCS levels II and II used to approximate the expected differences between treatment groups. Assuming a common standard deviation of 1,580 average strides/day, a sample size of 24 will have 90% power to detect a difference in average strides/day between treatment groups as small as 1,510 strides/day. In the event that we experience dropout, the primary analysis of each aim will still have > 80% power to accommodate as high as a 25% dropout rate (n=19 per group).

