Data Analysis Plan: The primary analysis will compare differences in changes from baseline to 8 weeks post in mean response between the treatment and comparison group using a general linear model with blocking factors for intervention site and GMFCS levels as fixed factors. By employing a randomized block design, we can statistically account for any clinical heterogeneity of outcomes by study site and GMFCS levels should this occur. To gain insight into both short and long-term retention of treatment effects, response profiles over the 4 time points will be compared using a linear mixed effects model with sites and GMFCS level as blocking factors, treatment group and time as fixed effects factors, and subjects as a random factor. These models will be used for analysis of the primary and secondary response variables of Specific Aims 1 and 2. The outcomes of Specific Aim 3 will use similar analysis models but will include an additional factor to allow comparison between home and community walking activity as a separate analysis. To assess the potential impact of gender on study outcomes, gender will be included in each of the models as a fixed effect. If significant gender effects are observed, we will report both adjusted and unadjusted estimates of treatment effects to more fully reveal the role of gender. Type I error rate will be set at 0.05. The primary dataset for analysis is the intent-to-treat dataset consisting of all patients randomized to intervention. The Statistical Analysis System (SAS®), V9.4 will be used for statistical analysis using GLM and MIXED procedures.

Data Management and Fidelity: REDCap™ will be used for data management. REDCap™ is a secure application designed for building and managing databases to allow electronic data collection from multi-site studies and allows instantaneous access to data. [name] will provide oversight to extensive quality control checks incorporated into the data entry system, such as real-time validation rules (with automated data type and range checks) at the time of data entry, and tracking of critical study events, such as assessment and

intervention visits requiring physical oversight as described previously. Data management principles will be implemented to ensure the integrity, security, and confidentiality of all study-related data.

Project Timeline

Task:	Year 1			Year 2			Year 3			Year 4			Year 5		
Train Intervention/Assessment staff	X	X													
Seattle site visit by PI	X	X		X			X				X				

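### The primary analysis is labelled intent-to-treat on all randomised children, but as specified it is a complete-case analysis of those with an 8-week value

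*Combined protocol and SAP*

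**What the plan says.** The Data Analysis Plan defines the primary comparison as follows: "The primary analysis will compare differences in changes from baseline to 8 weeks post in mean response between the treatment and comparison group". The method is a general linear model in which site and GMFCS level enter as fixed blocking factors. Gender is added to each model as a fixed effect. The analysis set is then named: "The primary dataset for analysis is the intent-to-treat dataset consisting of all patients randomized to intervention". SAS "will be used for statistical analysis using GLM and MIXED procedures".

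A second model, a linear mixed model with subject as a random factor, has a different stated purpose: "To gain insight into both short and long-term retention of treatment effects, response profiles over the 4 time points will be compared". It is also to be applied to the primary response variable, but it is not the primary analysis. Its listed terms are site, GMFCS level, treatment group and time; a group-by-time term is not named.

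On loss of children, the Power Calculations say: "In the event that we experience dropout, the primary analysis of each aim will still have > 80% power", for dropout of up to 25%, given as 19 per group. The text gives no imputation, no missing-data assumption, no sensitivity analysis, and no statement on whether children who stop training are still assessed.

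**The concern.** A change score needs two measurements. A child who misses the post visit has no response in the primary model and leaves it, even if baseline and the 2- or 6-month values were recorded. The set that produces the primary p-value is then smaller than the set named in the plan, and the difference is not disclosed.

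The protection of randomisation is at stake. If the children who miss the post visit would have changed differently from those who attend, the estimate no longer describes all randomised children. The primary and retention analyses would also rest on different children at the same visit. The planned difference is 0.12 m/s, and Preliminary Studies cites 0.10 m/s as the minimal clinically important difference for gait speed, so there is little room for distortion.

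**Working it through.** **1. Who enters the primary model.** One response per child: change = 8-week value − baseline value. If either is missing, the row is omitted. As a mechanical check, a linear model with arm, site and GMFCS level was fitted to 48 simulated children, 10 of them without a change score; it used 38.

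**2. The plan's dropout figure.** Inputs from Power Calculations: 24 per group, 25% dropout, 19 per group remaining.
- 24 × 0.75 = 18, not 19. The loss implied by 19 is 1 − 19/24 = 20.8%.
- Outside the primary model: 48 − 38 = 10 children at the plan's figure, or 48 − 36 = 12 at a true 25%.

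**3. The plan's power figure.** The primary outcome is stated to have "90% power to detect a difference of 0.12 m/s given a common standard deviation of 0.167 m/s" at 24 per group, two-sided 0.05. The two-sample t calculation with those inputs gives 68.3%. With 0.127 m/s, the SD printed for fast gait speed, it gives 89.3%, so the two SDs look exchanged. That is a separate matter and this point does not depend on it. At 19 analysed per group:

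| Outcome | SD used | Power |
|---|---|---|
| Self-selected gait speed, 0.12 m/s | 0.167 (printed) | 57.8% |
| Self-selected gait speed, 0.12 m/s | 0.127 | 80.9% |
| Peak power, 0.819 W/kg | 0.485 | 99.9% |
| Fascicle length, 1.55 cm | 1.61 | 82.3% |
| Strides per day, 1,510 | 1,580 | 81.8% |

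Apart from the SD question, the claim of more than 80% is reproduced by taking 19 as the number analysed. That is consistent with lost children leaving the primary analysis.

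**4. When the complete-case estimate is unbiased.** The model adjusts for site, GMFCS level and gender. Loss that depends only on those factors and on arm does no harm if effects are additive. A simulation with assumed values illustrates this: true difference 0.12 m/s, change depending on GMFCS level, PT3 loss of 5, 20 and 50% across levels I to III, comparison loss 10%. The adjusted estimate was 0.120 and the unadjusted 0.130. Harm arises when, within those strata, missing the post visit is related to the change.

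**5. Precision gained from the four-visit model.** Assumptions: 24 per arm, 18 with all visits, 6 without the post visit, equal within-child correlation ρ between visits, covariance known, separate arm means at each visit.
- If none of the 6 returns, they contribute baseline only. In units of the single-visit variance, the variance of an arm's mean change is (1 − ρ²)/18 + (1 − ρ)²/24, against 2(1 − ρ)/18 for complete cases. The reduction is 0.125 × (1 − ρ): 5.0% at ρ = 0.6, 3.1% at 0.75, 1.3% at 0.9.
- If 3 of the 6 return at 2 and 6 months, generalised least squares with the same covariance gives 7.3%, 6.3% and 5.4%.

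**6. Size if the missing children did not improve.** Inputs: PT3 gain 0.16 m/s (pilot data in Preliminary Studies); comparison gain 0.16 − 0.12 = 0.04 m/s (derived); gain of zero in children without a post value (assumed). All-randomised difference = 0.16 × (1 − PT3 loss) − 0.04 × (1 − comparison loss).

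| PT3 loss | Comparison loss | Difference (m/s) |
|---|---|---|
| 10% | 25% | 0.144 − 0.030 = 0.114 |
| 10% | 10% | 0.144 − 0.036 = 0.108 |
| 25% | 25% | 0.120 − 0.030 = 0.090 |
| 25% | 10% | 0.120 − 0.036 = 0.084 |

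At the plan's 19 per group the figure is 0.12 × 19/24 = 0.095. If missing children change like the observed children in their arm, it stays at 0.12.

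**The case against.** The strongest reply is that most of intent-to-treat survives. Nothing in the plan removes a child who stops training but attends the post assessment; that child is analysed in the assigned arm. A reader might infer a completer or per-protocol analysis, and the documents do not support that. The defect is confined to children without an 8-week value.

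Two further inferences go too far. The 25% is a rate that the power is said to tolerate, not a forecast of loss. The dropout sentence is a sizing contingency and not an analysis rule: it agrees with case deletion but does not prescribe it. Deletion is inferred from the model and from the absence of any missing-data rule.

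It can also be said that GMFCS adjustment already protects against loss related to functional class, which is correct, and that the mixed model will be fitted to gait speed anyway. That is also correct, but it is assigned to retention, so it does not govern the primary conclusion.

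Finally, the precision gain is modest. With the covariance estimated rather than known, a simulation gave about 2 to 5% when half of the missing children return and about 1 to 3% when none do. This stands: precision is not the main reason for the change. The reasons are that the label should match the analysis and that the missingness assumption should be weaker and stated.

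**Conclusion.** The point holds. The named analysis set and the specified primary model cannot both apply once a post value is missing. As written, the primary analysis is complete-case, leaving out 10 of 48 children at the plan's own figure or 12 at a true 25%.

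The mixed model weakens the assumption: loss may then also depend on the baseline value and on other observed visits. It does not correct loss that depends on unobserved response. A reader might take the 0.084 to 0.114 m/s range as an estimate of bias in this trial. It is not: it follows from an assumed zero gain in every child without a post value, and missing a visit is not evidence of no response. It shows only that an unstated assumption could move the result across the 0.10 m/s mark. Under that assumption with equal loss, this happens when 0.12 × (1 − loss) falls below 0.10, that is, above 1/6 or 4 of 24 per arm.

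**What to change.** In the Data Analysis Plan:

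1. Take the primary contrast, the arm difference in change from baseline to 8 weeks, from the four-visit mixed model. Include baseline as one of the responses, a group-by-time term, site and GMFCS level, and keep the planned gender term. Include every randomised child with at least one measured value, and report how many have none.
2. State that this analysis assumes data missing at random given the observed visits and model factors.
3. Keep the general linear model on observed changes as a supporting analysis, labelled 'complete cases'.
4. Add one sensitivity analysis that lowers the assumed gain of children without a post value in steps, for example down to zero, separately by arm.

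The cost is revised wording, a few lines of PROC MIXED code and a little more analysis work, with no new data. The downside is reliance on a missing-at-random assumption that cannot be verified, which is why step 4 is needed. A child with baseline only will add little to the contrast, and a child with no measurement remains outside it.
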